6. RATIONALE FOR DOSE

As of July 1st, 2014, 51 AML patients (combined ARO-004 study and ARO-005 study) have received crenolanib monotherapy. Among these 51 AML patients, the first 26 patients received 100 mg TID and the rest 25 patients received 200 mg/m2/day. PK parameters are available in all 26 patients at 100 mg TID and in 16 of 25 patients at 200 mg/m2/day.

PK analysis showed the following: (1) The median planned dose intensity at 200 mg/ m2/day (based on patient BSA) was 340 mg/day (range 300-400mg/day), which is approximately 11% higher than that at 100 mg TID (300 mg/day). (2) The median delivered dose intensity taking all dose reductions and dose delay into account was 314 mg/day (range 214-397 mg/day) at 200 mg/m2/day and 276 mg/day (range 204-298 mg/day) at 100 mg TID, respectively. (3) The median Day 15 trough level in patients treated with 200 mg/m2/day were similar to that of patients who received 100 mg TID [median 363 nM (range 40.6-3134) vs. median 419 nM (range 74-3720 nM)]. This suggests that there is no significant difference in median drug exposure among these two dosing groups (Figure 6-2), and more patient convenience within the 100 mg TID.

[figure not shown]
Figure 6-1. Day 15 Crenolanib Trough Levels (100 mg TID and 200 mg/m²/day)

Thus, a fixed dose regimen of 100 mg TID will be utilized for future clinical studies. Dose reductions to 80 mg TID and 60 mg TID will be applied should certain toxicities emerge in study individuals.

Serum concentrations of crenolanib in AML patients following a single dose of 100 mg is shown in Figure 6-3.

Figure 6-2. Serum Concentrations of Crenolanib following Single Dose (100 mg) in AML Patients

^{*}The median concentration for each time point is depicted by the thick black line.

7. STUDY DESIGN

This is a Phase II open label study of crenolanib besylate given at 100 mg TID (preferably every eight hours) continuously until one of the criteria for study discontinuation is fulfilled. Study drug should be taken at least 30 minutes prior to or following a meal. Patients will complete a daily diary to record the date, time, and amount (number of tablets) of crenolanib taken and relation to eating schedule (Appendix IV).

The study will enroll 2 different cohorts of patients in parallel.

Cohort A: Will enroll AML patients with FLT3 activating mutations who have progressed on one or more prior chemotherapy regimen who have not received previously a FLT3 TKI

Cohort B: Will enroll AML patients with FLT3 activating mutations whose leukemia has progressed and have received prior therapy with one or more FLT3 TKIs.

Cycles will be repeated approximately every 28 days, and therapy will be continued until clinically significant disease progression or documentation of unacceptable toxicity as determined by the investigator. If the drug is discontinued for toxicity, patient should be reassessed until toxicity has resolved.

In the setting where hematopoietic stem cell transplant is anticipated study drug will be discontinued at least 72 hours prior to start of conditioning.

Counting Cycle Days: If drug is held or a dose missed, the missed/held dose should not be made up. Dosing will resume with the next scheduled dose. The patient should enter in the diary the doses missed. If drug is held for a day or more, the counting of cycle days should continue as if uninterrupted. The start of cycle 1 is denoted by the ingestion of study drug. The scheduled procedures/visits should comply with the study calendar regardless of amount of study drug administered in a 28 day cycle.

8. PATIENT SELECTION

Patients must have baseline evaluations performed within 14 days prior to the first dose of study drug and must meet all inclusion and exclusion criteria. The exception to this is determination of FLT3 mutation status which can be done within 30 day screening period. Results of all baseline evaluations must be reviewed by the Principal Investigator or his/her designee prior to enrollment of that patient. In addition, the patient must be thoroughly informed about all aspects of the study, including the study visit schedule and required evaluations and all regulatory requirements for informed consent. The written informed consent must be obtained from the patient prior to initiating treatment. The following criteria apply to all patients enrolled onto the study unless otherwise specified.

8.1 **Inclusion Criteria**

- 1. Confirmed primary with primary AML relapsed or refractory after prior therapy, AML secondary to antecedent chemotherapy or radiation therapy, or AML due to prior myelodysplastic syndrome (MDS)/myeloproliferative neoplasm (MPN) as defined by WHO criteria with the presence of either FLT3-ITD and/or other FLT3 activating mutations, whose leukemia has recurred after prior chemotherapy but never received a FLT3 inhibitor (Cohort A) or whose leukemia has progressed after prior therapy and have history of prior exposure to one or more FLT3 TKIs (Cohort B).
- 2. Patients with secondary AML should have failed no more than two (2) prior cytotoxic chemotherapy containing regimens.
- 3. Patients with antecedent MDS/MPN defined by WHO criteria, without any prior therapy for AML regardless of the number of therapies for MDS/MPN.
- 4. Patients with primary AML should have received no more than two (2) prior cytotoxic drug containing salvage regimens. Reinduction with the same regimen or a stem cell transplant following salvage therapy is not considered a separate salvage regimen. Change of drugs will be considered a salvage regimen. Unlimited FLT3 TKI therapy (even in combination with cytotoxics/hypomethylating agents) is allowed for patients enrolled in cohort B.
- 5. Patients must have tested positive for FLT3-ITD and/or other FLT3 activating mutations within the 30 day screening period.
- 6. Males and females age \geq 18 years
- 7. ECOG PS 0-2
- 8. Adequate liver function, defined as bilirubin $\leq 1.5x$ ULN, ALT $\leq 3.0x$ ULN, and AST $\leq 3.0x$
- 9. Adequate renal function, defined as serum creatinine ≤1.5x ULN
- 10. Recovery from non-hematological toxicities of prior therapy (including HSCT) to no more than grade 1 (except alopecia)
- 11. Subjects should have received no anti-leukemic therapy except hydroxyurea prior to the first dose of crenolanib as follows: for 14 days for classical cytotoxic agents and for five times the half-life for FLT3 inhibitors and antineoplastic agents that are neither cytotoxic nor FLT3 inhibitors (e.g. hypomethylating agents or MEK inhibitors) Refer to Appendix XVI for half-life information and drugs considered as FLT3 inhibitors for purposes of this trial.

12.

- 12.1 Negative pregnancy test for women of childbearing potential (WOCBP). WOCBP must practice contraception. Acceptable methods of contraception are double barrier methods (condoms with spermicidal jelly or foam and diaphragm with spermicidal jelly or foam), oral, depo provera, or injectable contraceptives, intrauterine devices, and abstention.
- 12.2 Male patients with female partners who are of childbearing potential: Recommendation is for male and partner to use effective contraceptive methods, as described above, during the study.
- 12.3 Women considered not of childbearing potential include any of the following: no menses for at least 5 years or menses within 5 years but amenorrheic for at least 2 months and luteinizing hormone (LH) and follicular stimulating hormone (FSH) values within normal range (according to definition of postmenopausal for laboratory used) or bilateral oophorectomy or radiation castration and amenorrheic for at least 3 months or with bilateral tubal ligation.
- 13. Able and willing to provide written informed consent.

8.2 Exclusion Criteria

- 1. Absence of a FLT3 activating mutation
- 2. <5% blasts in blood or marrow at screening
- 3. Concurrent chemotherapy, or targeted anti-cancer agents, other than hydroxyurea.
- 4. Patient with concurrent severe and/or uncontrolled medical conditions that in the opinion of the investigator may impair the participation in the study or the evaluation of safety and/or efficacy.
- 5. HIV infection or active hepatitis B or C (defined as positive hepatitis B surface antigen positive or hepatitis C antibody positive)
- 6. Known clinically active central nervous system (CNS) leukemia
- 7. Patients who are <30 days of a HSCT.
- 8. Subjects who have clinically significant graft-versus-host disease requiring treatment, and/or have >Grade 2 persistent non hematological toxicity related to the transplant
- 9. Prior crenolanib treatment for non-leukemic indication
- 10. Major surgical procedures within 14 days of Day 1 administration of crenolanib.
- 11. Unwillingness or inability to comply with protocol.

9. TREATMENT PLAN

9.1 General

The study will enroll patients with primary AML relapsed/ refractory after prior therapy, secondary AML (due to prior chemo- or radiation therapy) or prior transformed MDS/MPN with FLT3 activating mutations. Patients will be treated with crenolanib three times daily, preferably every eight hours, continuously until they fulfill one of the criteria for study discontinuation. The objective will be to administer crenolanib at full dose starting at 100 mg TID. Other dose levels will be used for dose adjustments for toxicity (refer to section 10) during therapy. The only exception to this will occur on course 1 day 1, when doses 2 and 3 will be held in order to analyze the pharmacokinetics of the first dose administered out to 24 hours.

Patients currently enrolled at 100mg TID (protocol v1.1) may be dose escalated based on BSA, see table 10.2.

Up to 70 evaluable patients will be enrolled on this study: 30 patients in Cohort A and 40 patients in Cohort B. Patients receiving less than 28 days of study dug will be replaced for efficacy evaluation. All patients will be assessed for toxicity.

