9.2 Schedule

Protocol: ARO-005

Patients will be treated according to the following schedule:

- The starting dose will be 100 mg TID. Dose reductions for adverse events are listed in table 10.2.
- Dose reduction guidelines for adverse events are listed in table 10.2 and 10.3 in Section 10.2. Dose reductions beyond those mentioned in these tables or different than those specified, should be discussed with the sponsor and documentation of the justification recorded.
- One cycle of therapy is defined as 28 consecutive days regardless of whether study drug is taken or not.
- Subsequent cycles may be delayed for recovery of toxicity. Delays in start of subsequent cycles greater than 8 weeks will be acceptable only for patients who are deriving clinical benefit and after determination of the principal investigator of potential risk/benefit ratio.
- If prolonged (more than 60 days) grade 4 neutropenia or thrombocytopenia with evidence of a hypocellular marrow (marrow cellularity less than 5% without evidence of leukemia) is observed, protocol treatment may be interrupted until recovery to ANC $> 0.5 \times 10^9$ /L and platelets $> 25 \times 10^9$ /L . If the peripheral counts do not recover ANC $< 0.5 \times 10^9$ /L and/or platelets $< 25 \times 10^9$ /L but there is evidence of residual leukemia in the bone marrow, subsequent cycles can be administered at the discretion of the investigator.
- For patients who discontinue therapy, the reason for treatment discontinuation will be captured.

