9.3 Crenolanib Administration

- Prophylactic antiemetic therapy is recommended to be used as needed for nausea and/or vomiting.
- If a dose is missed or vomited, it should not be taken again. The next dose should not be increased to account for missing a dose. The patient should take the next regular dose at the regularly scheduled time.

9.4 **Duration of Therapy**

Treatment may continue until one of the following criteria applies:

- 1. Clinically significant progressive disease, or
- 2. Intercurrent illness that in the opinion of the investigator prevents further administration of treatment, or
- 3. Patient request, or
- 4. General or specific changes in the patient's condition render the patient unacceptable for further treatment in the judgment of the investigator, or
- 5. Unacceptable toxicity that in the opinion of the investigator makes it unsafe to continue therapy, or
- 6. Treatment interruption due to toxicity that has not recovered to at least grade 1 within 8 weeks

It is planned that up to a total of 12 cycles of therapy will be administered for patients deriving benefit from this regimen. Continuation of therapy for patients completing 12 cycles of therapy may be considered on a case by case basis after discussion with the sponsor's medical monitor.

A minimum of 1 full course (defined as the administration of crenolanib for 28 days) will be required for a patient to be considered as having received an adequate trial to evaluate efficacy. Patients who do not complete one cycle of crenolanib therapy will be replaced. All patients receiving at least one dose of study drug will be considered evaluable for toxicity.

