13.2 Evaluation during Treatment

- 1. Physical exam at the start of each cycle (\pm 4 days) for the first 2 cycles, then every 2 cycles and documentation of all concomitant medications.
- 2. CBC, platelet count, differential (differential may be omitted if WBC is $<0.5 \times 10^9/L$) twice weekly (at least 24 hours apart) for the first two weeks of cycle 1, once weekly (\pm 3 days) for the second two weeks of cycle 1, bi-weekly (\pm 4 days) for the second cycle and once a month thereof from cycle 3 until cycle 12 (\pm 14 days).
- 3. Creatinine, total bilirubin, ALT, AST, twice weekly (at least 24 hours apart) for the first two weeks of cycle 1, once weekly (±3 days) for the second two weeks of cycle 1, bi-weekly (± 4 days) for the second cycle and once a month thereof from cycle 3 until cycle 12 (± 14 days).
- 4. Bone marrow aspiration x 2 should be taken at these timepoints: cycle 2 day 1 (+4 days), then cycle 3 day 1 (+/- 7 days), then every 3 cycles (+/- 1 cycle) as long as criteria for CR is maintained. At loss of CR, bone-marrow aspiration would be performed only as clinically indicated to exclude toxicity issues like persistent pancytopenia due to study drug vs from progressive AML.

- 5. Peripheral blood for correlative studies will be drawn on day1 at the following time points: pre dose and at 30 (\pm 10), 60 (\pm 15), 120 (\pm 15) minutes, 4 (\pm 1) hours, 8 (\pm 2), and 24 (\pm 6) hours after crenolanib administration. Blood samples will also be drawn on day 15 of cycle 1 at the following time points: pre dose, 30 (\pm 10) minutes, and 4 (\pm 1) hours after crenolanib administration. Blood samples will also be drawn on day 1 cycle 2 (±2 days), day 1 cycle 3 (± 2 days) at the following time points: pre dose, 4 ± 1 hours after crenolanib administration. On subsequent courses, samples may be obtained at the discretion of the investigator, predose, and whenever possible every 2-4 cycles.
- 6. For patients that remain on study with no significant toxicity for more than 12 months, subsequent evaluations during study may be modified after discussion with the sponsor. These may include a decrease in frequency of bone marrow aspirations to every 6-12 months (or as clinically indicated), correlative studies to every 6-12 months (or suspension of sample collection for correlative studies), and other laboratory tests to once every cycle.

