16. STATISTICAL CONSIDERATIONS

16.1 Determination of Sample Size

The primary endpoint of the study is the overall response rate to crenolanib. The outcome may be different for patients with or without the previous FLT3 TKI therapy. Therefore, patients will be stratified according to whether they have recurred after prior chemotherapy without a FLT3 TKI treatment or they have progressed after prior therapy with a FLT3 TKIs.

Based on the promising results observed to date, the sample size for each cohort will be expanded to include a total of 30 patients in Cohort A and 40 patients in Cohort B. Such additional patients will permit a more accurate assessment of the efficacy and safety of crenolanib in these populations. The total sample size for the two cohorts is 70 patients.

Cohort B (N=40): Two parallel Simon minimax two-stage Phase II designs will be used for the two cohorts of patients. For the patients who progressed after prior chemotherapy with FLT3 TKI, the null response rate will be 5%, and target response rate will be 20%. With alpha of 0.05 and beta of 0.08, the first stage will require 28 patients. If there is 1 or no patient responding, the trial will be stopped. If 2 or more out of the first 28 patients respond, accrual will continue until a total of 40 patients have been enrolled. At the end of the study, if 5 or more patients out of 40 respond, the regimen will be considered active. With this design, the probability of early termination is 59% if the true response rate is only 5%.

Cohort A (N=30): For the patients who progressed after prior chemotherapy without FLT3 TKI, the null response rate will be 5%, and target response rate will be 30. With alpha of 0.06 and beta of 0.01, the first stage will require 24 patients. If there is 1 or no patient experiencing the response, the trial will be stopped. If 2 or more out of the first 24 patients respond, accrual will continue until a total of 30 patients have been enrolled. At the end of the study, if 4 or more patients out of 30 respond, the regimen will be considered active. With this design, the probability of early termination is 66% if the true response rate is only 5%.

The method of Thall, Simon, and Estey will be employed to perform interim safety monitoring. We will assume a Beta (0.6, 1.4) prior distribution for the toxicity rate which in particular has mean of 30%. The toxicity is defined as any grade 3 or greater non-hematologic toxicities attributed to the study drug.

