16.3 Statistical and Analytical Plans

The primary end-point is overall response rate. The overall response rates in the two cohorts will be evaluated along with its 95% confidence interval. Analysis of secondary endpoints will be predominantly descriptive statistics and will be interpreted as being exploratory and hypothesis generating. Progression free survival (PFS) and overall survival (OS) will be estimated using the method of Kaplan-Meier. Cox regression models will be used to determine the relationship with the time-to-events (e.g. PFS and OS) and the potential prognostic factors. Exploratory logistic regression will be used to identify the prognostic factors that are significantly correlated with the response rate.

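### The 28-day replacement rule can take early treatment failures out of the primary response rate, and section 16 defines no all-treated efficacy population

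*Combined protocol and SAP*

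**What the plan says.** Section 9.1 plans up to 70 evaluable patients, 30 in Cohort A and 40 in Cohort B, and adds: "Patients receiving less than 28 days of study dug will be replaced for efficacy evaluation". Section 9.4 says the same: "Patients who do not complete one cycle of crenolanib therapy will be replaced". It also states the condition for being evaluable for efficacy: "A minimum of 1 full course (defined as the administration of crenolanib for 28 days) will be required for a patient". Patients with at least one dose count for toxicity. No such population is defined for efficacy.

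Section 9.4 lists progression, intercurrent illness, patient request and unacceptable toxicity among the reasons to stop. The synopsis adds death. The replacement rule excepts none of them.

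Section 16.1 sets the Simon designs: 5% null in both cohorts, with targets of 20% (B) and 30% (A). Section 16.3 gives the analysis in one line, without a denominator: "The overall response rates in the two cohorts will be evaluated along with its 95% confidence interval".

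The unit of the rule is also unsettled. Section 9.2 says: "One cycle of therapy is defined as 28 consecutive days regardless of whether study drug is taken or not". Section 9.4 asks for 28 days of administration.

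**The concern.** A patient who progresses or dies on day 20 would be replaced instead of counted as a failure. The loss is likely to be selective. CR, CRi and PR in section 14 all depend on a marrow result, and the first scheduled on-treatment marrow (section 13.2) is on day 1 of cycle 2. Few patients who stop before day 28 would therefore have a documented response.

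Two things are at stake. The first is the estimate: the objective in section 1.1 concerns relapsed or refractory patients with FLT3 mutations, not those who stay on drug for 28 days. The second is the decision rule: the pass marks (5 of 40, 4 of 30) and the stage 1 futility stops have their stated error rates only if the null rate applies to the patients who are counted. The plan does not say that it does.

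**Working it through.** **Inputs from section 16.1.** Cohort B: stop if at most 1 of 28 respond, active if at least 5 of 40. Cohort A: stop if at most 1 of 24, active if at least 4 of 30.

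**Method.** Exact two-stage binomial. With n1 patients in stage 1, X1 stage 1 responders, X2 stage 2 responders, futility limit r1 and pass mark r:

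- Probability of early termination (PET) = P(X1 ≤ r1)
- P(declared active) = Σ over x > r1 of P(X1 = x) × P(X2 ≥ r − x)

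**The plan's own figures.** Both designs reproduce.

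| Cohort | alpha | power | PET at 5% | Stated alpha, beta, PET |
|---|---|---|---|---|
| B | 0.0472 | 0.921 | 0.588 | 0.05, 0.08, 59% |
| A | 0.0599 | 0.990 | 0.661 | 0.06, 0.01, 66% |

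**Assumptions for the effect of replacement.** The documents give neither d, the fraction of treated patients who stop before 28 days, nor k, the response rate of early leavers relative to the all-treated rate. Replaced patients are taken to be left out of the count. If the all-treated rate is 5%, the rate among counted patients is

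q = 0.05 × (1 − k·d) / (1 − d).

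At d = 20%: q = 0.05/0.8 = 6.25% for k = 0, and q = 0.05 × 0.9/0.8 = 5.63% for k = 0.5.

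**Type I error when the 5% null refers to all treated patients (B / A).**

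| d | k = 0 | k = 0.5 | k = 1 |
|---|---|---|---|
| 0 | 4.7% / 6.0% | 4.7% / 6.0% | 4.7% / 6.0% |
| 10% | 6.8% / 8.2% | 5.7% / 7.0% | 4.7% / 6.0% |
| 20% | 10.1% / 11.3% | 7.1% / 8.4% | 4.7% / 6.0% |
| 30% | 15.2% / 16.1% | 9.2% / 10.5% | 4.7% / 6.0% |

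**Futility stop at d = 20%.** PET under the null falls from 59% to 47% (k = 0) or 53% (k = 0.5) in B, and from 66% to 55% or 61% in A.

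**Estimate at d = 20%.** A true all-treated rate of 20% appears as 0.20/0.8 = 25% (k = 0) or 0.20 × 0.9/0.8 = 22.5% (k = 0.5). A bare pass of 5/40 = 12.5% in B takes 40/0.8 = 50 treated patients. If no early leaver responds, it is 5/50 = 10% of those treated.

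**Patients treated at d = 20%.** If replacements are added beyond 70, the maximum is 70/0.8 = 87.5, about 88. Under the null with k = 0 the expected number is [28 + 12 × (1 − 0.4705) + 24 + 6 × (1 − 0.5524)]/0.8 = 76.3.

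**The case against.** The strongest reply is that replacing a patient is not the same as deleting that patient from the reported rate. Section 16.1 continues accrual to totals of enrolled patients, and section 16.4 sets no minimum compliance for inclusion in efficacy analyses. This stands in part, since the final denominator is nowhere stated. But neither line defines an all-treated population, the compliance line concerns tablet counts, and section 9.1 replaces these patients specifically for efficacy. Two analysts could report different primary results from the same data.

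A second reply is that a design for evaluable patients is legitimate if the null and targets describe such patients. That is true, and alpha then holds. Section 16.1 does not say so, and the result would then apply only to completers.

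A third is that the inflation is conditional and can be small: at d = 10% and k = 0.5 it is 5.7% and 7.0%, in a study the synopsis calls a pilot. That is fair. The stronger ground is the undefined denominator. Section 16.3 reserves the exploratory label for secondary endpoints, and the primary endpoint carries a formal active/inactive rule.

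A fourth is that early leavers may respond more often, for example patients who stop drug before transplant conditioning (section 7). With k = 2 and d = 20%, q = 0.05 × 0.6/0.8 = 3.75%, so the bias reverses. That is possible, but it means the rule can also discard true responders. An all-treated denominator corrects both errors.

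Finally, the cycle definition in 9.2 may serve scheduling only. Even so, whether a patient with held doses has completed a cycle is left open.

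**Conclusion.** The concern holds and must be fixed before the primary analysis. As written, the only efficacy rule in the plan replaces early failures, and nothing in section 16 returns them to the denominator.

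The upward bias needs two conditions: replaced patients are not counted, and they respond less often than completers. The type I inflation also needs the 5% null to refer to all treated patients. Across d of 10% to 30% and k of 0 to 0.5, type I error is then 5.7% to 15.2% in Cohort B and 7.0% to 16.1% in Cohort A. With k = 1 there is neither bias nor inflation. With a null for completers there is no inflation, but the go/no-go conclusion is narrower than the stated objective.

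**What to change.** - Define the primary efficacy population in section 16 as all patients who receive at least one dose, and count anyone without a documented CR, CRi or PR as a non-responder.
- Apply the Simon counts (28 then 40 in B, 24 then 30 in A) to treated patients, and withdraw the replacement rule in 9.1 and 9.4 for the primary analysis.
- Report 28-day completers as a supportive analysis.
- State in 16.1 that the null and target rates refer to all treated patients, and restate power.
- Align the evaluable wording in 9.1, the enrolled wording in 16.1 and the compliance sentence in 16.4, and reconcile the cycle definition in 9.2 with the 28 days of administration in 9.4.

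**Cost.** Wording, probably a somewhat lower reported response rate, and possibly lower power. If the 20% and 30% targets were meant for completers and early leavers do not respond, the all-treated targets become 0.20(1 − d) and 0.30(1 − d). With the same counts, power is then:

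| d | B | A |
|---|---|---|
| 0 | 92% | 99% |
| 10% | 87% | 98% |
| 20% | 78% | 95% |
| 30% | 67% | 90% |

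The sponsor would have to accept and restate these figures or revisit the sample size. In return, no replacement patients are treated and the total stays within 70, the limit to which the safety monitoring rule in 16.1 is specified.
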